## 14. Additional Effectiveness Analyses

All additional effectiveness analyses will be based on the AAS observed data unless otherwise stated.

### 14.1 Visual Acuity Analyses

The visual acuity exploratory endpoints are as follows:

- Photopic monocular logMAR BCDVA, [REDACTED] DCIVA (66 cm), and DCNVA in first operative eyes at all applicable visits
- Mesopic monocular logMAR [REDACTED], DCIVA (66 cm), and DCNVA in first operative eyes at all applicable visits
- Photopic binocular logMAR BCDVA, [REDACTED] DCIVA (66 cm), and DCNVA at all applicable visits
- Mesopic binocular logMAR [REDACTED] DCIVA (66 cm), and DCNVA at all applicable visits
- Photopic monocular logMAR UCDVA, [REDACTED], UCIVA (66 cm), and UCNVA in first operative eyes at all applicable visits
- Photopic binocular logMAR UCDVA, [REDACTED], UCIVA (66 cm), and UCNVA at all applicable visits
- Photopic monocular logMAR [REDACTED] and BCNVA in first operative eyes at all applicable visits
- Photopic binocular logMAR [REDACTED] and BCNVA at all applicable visits

The above endpoints will be summarized by treatment group and visit using continuous descriptive statistics. Additionally, photopic monocular logMAR BCDVA, DCNVA, and DCIVA (66 cm) in first operative eyes at Month 12 (Visit 5) will be analyzed by repeating the primary and secondary effectiveness analyses as appropriate.

A visual acuity variable will be summarized categorically by logMAR score within the following visual acuity ranges:

- 0.00 logMAR or better
- 0.10 logMAR or better
- 0.20 logMAR or better
- 0.30 logMAR or better
- Worse than 0.30 logMAR

A visual acuity variable will be summarized categorically by Snellen score within the following visual acuity ranges:

- 20/20^-2 or better ( $\leq 0.04$  logMAR)
- 20/25 or better ( $\leq 0.14$  logMAR)
- 20/32 or better ( $\leq 0.24$  logMAR)
- 20/40^-2 or better ( $\leq 0.34$  logMAR)
- Worse than 20/40^-2 ( $> 0.34$  logMAR)

The frequency and percentage of subjects achieving the above logMAR visual acuity thresholds for all endpoints listed above will be presented by treatment group and visit. Similar analyses will also be performed using Snellen visual acuity thresholds.

The frequency and percentage of subjects achieving the above logMAR visual acuity threshold at all distances for photopic binocular logMAR UCDVA, UCIVA (66 cm), and UCNVA will also be presented. Similar analyses will also be performed using Snellen visual acuity thresholds.

## 14.2 Defocus Curves

Defocus curve testing will be performed under photopic conditions at a test distance of 4 m at Month 6 (Visit 4) and Month 12 (Visit 5). [REDACTED]

[REDACTED] Each subject will be defocused with spherical lenses from +2.00 D through -4.00 D over the subject's manifest distance correction in -0.50 D increments.

Monocular and binocular defocus curves from Month 6 (Visit 4) and Month 12 (Visit 5) based on the Best Case Set will be summarized by treatment group and visit utilizing continuous descriptive statistics. Defocus curve summaries by treatment group will also be presented for each of the following post-operative photopic pupil size groups:

- Small (< 2.5mm)
- Medium (2.5mm to  $\leq$  4mm)
- Large (> 4mm)

For summaries of binocular defocus curves by pupil size, the average pupil size computed over both eyes will be used to determine the pupil size subgroup.

The defocus curve means will be plotted for each treatment group and for each pupil size group with error bars representing one standard deviation.

### **14.3 Spectacle Independence**

The Patient-Reported Spectacle Independence Questionnaire (PRSIQ) will be used to assess subjective spectacle independence at Month 6 (Visit 4). For distance vision (5 or more feet away), intermediate vision (1.5 to 5 feet away), and near vision (less than 1.5 feet away), the PRSIQ asks the subject the following questions:

- During the last 7 days, did you need glasses or contacts?
- During the last 7 days, how often did you wear glasses or contacts?
- During the last 7 days, were you able to function comfortably without glasses or contacts?

The response options for the “need” item are “Yes” (1) and “No” (2). The response options for the “wear” and “function” items are “All of the time” (1), “Most of the time” (2), “Some of the time” (3), “A little of the time” (4), and “None of the time” (5).

The responses of subjects for each item will be summarized by treatment group using discrete summary statistics.

## **15. Safety Analyses**

All safety analyses will be conducted using the Safety Set unless otherwise stated.

### **15.1 Primary Safety Analyses**

The co-primary safety endpoints are:

- Cumulative rate of SSIs related to the optical properties of the IOL in first operative eyes through Month 12 (Visit 5)
- Mean monocular distance contrast sensitivity (mesopic with and without glare at 1.5, 3, 6, and 12 cpd measured at 2.5m, and photopic with and without glare at 3, 6, 12, and 18 cpd, measured at 2.5 m) in first operative eyes at Month 12 (Visit 5)

The analyses of co-primary safety variables will be based on first operative eyes and repeated as supportive analyses using second operative eyes as well as all operative eyes.

Secondary surgical interventions related to the optical properties of the IOL will be evaluated using discrete summary statistics. Noninferiority of FINEVISION HP IOL compared to AcrySof® SN60AT [REDACTED] IOL in the proportions of first operative eyes with secondary surgical interventions related to the optical properties of the IOL will be evaluated using two-sided 90% Farrington method CIs around the difference in proportions between the FINEVISION HP IOL and AcrySof® SN60AT [REDACTED] IOL. If the upper limit of the CI is less than 0.014 (1.4%), then  $H_{01s}$  will be rejected in favor of  $H_{11s}$ , and the FINEVISION HP IOL will be considered statistically non-inferior to the AcrySof® SN60AT [REDACTED] IOL in rate of SSIs related to optical properties of the IOL.

SAS® code similar to the code below will be used to compute the Farrington CIs:

```
proc freq data = indata;
  table TRTAN * resp / nocol nopercent riskdiff(noninf margin = 0.014
method = fm column = 1) alpha = 0.05;
  ods output CrossTabFreqs = freqs(where = (resp = "Y")) PdiffNoninf =
cis;
run;

data freqs;
  set freqs;
  freq = Frequency;
  pct = RowPercent;
run;

/* Adjust CIs to convert limits to percentages and convert diff estimate, CI
for p_control - p_test to diff estimate, CI for p_test - p_control */
data cis;
  set cis;
  diff_pct = -100*Estimate;
  diff_ci_LCL = -100*UpperCL;
  diff_ci_UCL = -100*LowerCL;
run;
```

where

- TRTAN equals 1 for the test IOL (FINEVISION HP IOL) and 2 for the control IOL (AcrySof® SN60AT [REDACTED] IOL)
- resp equals "Y" if a subject has any SSIs related to the optical properties of the IOL or "N" if a subject has no SSIs related to the optical properties of the IOL.

Monocular best-corrected distance contrast sensitivity (mesopic with and without glare at 1.5, 3, 6, and 12 cpd measured at 2.5 m, and photopic with and without glare at 3, 6, 12, and 18 cpd, measured at 2.5 m) in first operative eyes based on the Best Case Set will be summarized by treatment group using continuous summary statistics. The treatment group difference (mean Test group contrast sensitivity minus mean Control group contrast sensitivity) in log units will be presented by testing condition and frequency. Additionally, for each testing condition and frequency, the 5th percentile for the control group log contrast sensitivity will be determined, and the number and percentage of subjects in the investigational arm who have achieved a log contrast sensitivity lower than this value will be reported.

As a subgroup analysis, the primary analysis of the cumulative rate of SSIs related to the IOL will be repeated for the following Pre-Operative Visit photopic pupil size subgroups: small (< 2.5 mm), medium (2.5 to ≤ 4mm), and large (> 4 mm). Similar subgroup analyses will be performed for mean monocular best-corrected distance contrast sensitivity at Month 12 (Visit 5) with subgroups based on photopic pupil size at Month 12 (Visit 5) for photopic lighting conditions or mesopic pupil size at Month 12 (Visit 5) for mesopic lighting conditions.

As poolability analyses, the co-primary safety endpoints will be summarized by treatment group and site using discrete or continuous summary statistics as appropriate.

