## 5.2 Primary Safety Variable Sample Sizes

### 5.2.1 SECONDARY SURGICAL INTERVENTIONS

For safety (based on ANSI Z80.12) 300 first operative eyes with FINEVISION HP IOL and 150 first operative eyes with AcrySof® SN60AT [REDACTED] IOL completing through Month 12 (Visit 5) yields approximately 80% power to reject  $H_{01s}$  in favor of  $H_{11s}$  and conclude the FINEVISION HP IOL is non-inferior to the AcrySof® SN60AT [REDACTED] IOL in SSIs related to the optical properties of the IOL, using a one-sided Farrington-Manning score test with an alpha level of 0.05 and assuming the true proportions of SSIs related to the optical properties of the FINEVISION HP IOL and of the AcrySof® SN60AT [REDACTED] IOL are both equal to 0.001, and a non-inferiority margin of 0.014 (1.4%). Similarly, ISO 11979-7 specifies that a minimum of 300 subjects should complete a clinical evaluation of an IOL to obtain appropriate specificity around AE and visual acuity rates.

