## 15.2 Secondary Safety Analyses

The secondary safety endpoints include the following:

- Rates of cumulative and persistent AEs in first operative eyes through Month 12 (Visit 5), compared to the ISO SPE rates as described in ISO 11979-7
- Visual disturbances using the QoV questionnaire and QoV Supplemental Questions at Month 12 (Visit 5)

The ISO defines cumulative adverse events as the “total number of adverse events that have occurred at any time up to a specified time point post-operatively” and a persistent adverse event as an “adverse event that is present at the conclusion of a clinical investigation”. Cumulative and persistent AEs from ISO 11979-7 Table E.2 will be summarized by AE and treatment group using discrete summary statistics separately for first operative eyes, second operative eyes, and all operative eyes. Cumulative AEs which occur at any time during the study will be counted. If a subject experiences a specific cumulative AE more than once during the study, they will only be counted once for that specific cumulative AE. Persistent AEs which are classified as ongoing at the time of study exit will be counted, and a subject will only be counted at most one time for a specific persistent AE.

The p-values from one-sided exact binomial tests comparing the observed AE rates to the SPE rates from Table E.2 will also be presented by treatment group. Additionally, cumulative and persistent adverse events will be summarized separately by age group (< 65 years vs. ≥ 65 years) and by site for first operative eyes, second operative eyes, and all operative eyes. The binomial test p-values will be computed as in the SAS® code below:

```
data ae_tbl;
  set ae_tbl;
  percent = 100*FREQ/N;
  pval = 1 - cdf('BINOMIAL', FREQ - 1, spe/100, N);
run;
```

where

- FREQ = number of unique eyes for each AE from ISO 11979-7 Table E.2

- $N$  = number of eyes in the Safety Set for each treatment group
- $spe$  = SPE rate for each AE from ISO 11979-7 Table E.2

The Quality of Vision (QoV) questionnaire will be used to assess subjective visual disturbances reported by subjects receiving IOLs. The QoV asks the subject to rate the frequency, severity, and degree of bothersomeness for 10 items/visual disturbances in their everyday life based on the past week. The rating scales for frequency, severity, and degree of bothersomeness are:

- Frequency: 0 (Never), 1 (Occasionally), 2 (Quite Often), 3 (Very Often)

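### The supportive all-operative-eyes safety analyses make no visible allowance for two eyes of one subject, and SAP 15.2 mixes subject and eye counts

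*SAP*

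**What the plan says.** SAP 4.1 assigns each subject one lens model for both eyes. The hypothesis on secondary surgical interventions (SSIs) related to the optical properties of the lens, H01s in SAP 3.5.2.1, is stated for first operative eyes. Its power in SAP 5.2.1 is also for first eyes: "300 first operative eyes with FINEVISION HP IOL and 150 first operative eyes with" the control lens.

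SAP 15.1 and Protocol 9.4.6 then have the co-primary safety analyses "repeated as supportive analyses using second operative eyes as well as all operative eyes". The only SSI analysis described is the two-sided 90% Farrington interval, judged against 0.014. The accompanying code defines the response per subject: yes if the subject has any such SSI.

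SAP 15.2 summarises the ISO 11979-7 cumulative and persistent adverse events separately for first, second and all operative eyes. It adds: "The p-values from one-sided exact binomial tests comparing the observed AE rates to the SPE rates". The code takes the number of unique eyes with the event as numerator and, as denominator, the "number of eyes in the Safety Set for each treatment group". The text of the same section says that a subject with a repeated event counts only once for that event.

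SAP 8.1 describes the second-eye and all-eyes results as supportive. The text directly after that is redacted.

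**The concern.** Two eyes of one subject share the patient, usually the surgeon, and here the lens model. Protocol 8.6 attributes an SSI to the optical properties when the subject cannot tolerate visual symptoms that spectacles do not adequately improve. That is a subject-level cause acting on two lenses of the same model, so bilateral events are plausible. Counting such eyes as independent observations doubles the apparent sample size without doubling the information.

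The consequence differs between the two analyses. For the SSI interval, the upper limit would be too low and could fall under 0.014 on data that fail by first eye. For the ISO p-values, which are upper-tail, a small value says that the rate exceeds the ISO safety and performance endpoint (SPE) rate, so ignored correlation produces false alarms. The conflict between counting subjects and counting eyes can push the ISO result the other way.

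**Working it through.** **Inputs.** From SAP 5 and 5.2.1: 334 test and 167 control subjects operated; 300 and 150 for power; margin 0.014; one-sided 0.05; true rates of 0.001. Assumed: both eyes implanted in every subject (668/334 or 600/300 eyes); within-subject correlation ρ from 0 to 1, since the documents give none; an SPE rate of 0.8%, since the ISO table is not reproduced.

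**1. The plan's own figure.** SAP 5.2.1 "yields approximately 80% power to reject" H01s, "using a one-sided Farrington-Manning score test with an alpha level of 0.05", with true proportions that "are both equal to 0.001".
- Null standard error at the constrained rates (0.01435 and 0.00035): SE0 = 0.00703.
- SE under the alternative: √[0.001 × 0.999 × (1/300 + 1/150)] = 0.00316.
- Power = Φ[(0.014 − 1.645 × 0.00703)/0.00316] = Φ(0.770) = 77.9%.
- Exact enumeration gives 77.2%; null variance at the boundary (0.014 and 0) gives 81.6%.

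These values bracket the stated power, so I do not dispute it.

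**2. SSI interval if each row is an eye.** With no control event the constrained rates are 0.014 and 0, so SE0 = √(0.014 × 0.986/n_test), z = (p̂ − 0.014)/SE0 and upper limit = p̂ + 1.645 × SE0.

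| Data, no control event | p̂ | SE0 | z | Upper limit | Below 1.4%? |
|---|---|---|---|---|---|
| First eye, 2/334 | 0.00599 | 0.00643 | −1.246 | 1.66% | No |
| Same two subjects, both eyes, 4/668 | 0.00599 | 0.00455 | −1.762 | 1.35% | Yes |
| First eye, 1/300 | 0.00333 | 0.00678 | −1.572 | 1.45% | No |
| Same subject, both eyes, 2/600 | 0.00333 | 0.00480 | −2.224 | 1.12% | Yes |

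Inverting the score test instead gives 1.79% and 1.33% for the first two rows, with the same pass or fail. Multiplying the all-eyes SE by √(1 + ρ) moves the 4/668 limit from 1.35% to 1.44% at ρ = 0.25, 1.52% at 0.5 and 1.66% at 1.

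**3. Error rate of the eye-level SSI rule.** Model: P(both eyes) = p[ρ + (1 − ρ)p], summed exactly over subjects, with true rates of 1.5% and 0.1% (a difference equal to the margin).

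| Subjects | ρ = 0 | ρ = 0.25 | ρ = 0.5 | ρ = 1 | First-eye test |
|---|---|---|---|---|---|
| 334/167 | 4.2% | 6.2% | 8.3% | 14.6% | 5.4% |
| 300/150 | 3.5% | 5.4% | 7.4% | 10.1% | 2.1% |

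**4. ISO binomial test, eyes over eyes.** With 668 eyes and a true rate equal to the assumed SPE rate of 0.8%, p < 0.05 first occurs at 10 eyes.
- ρ = 0: P(X ≥ 10; 668, 0.008) = 4.5%.
- ρ = 0.5: about 8%.
- ρ = 1: ten eyes are five subjects, and P(Y ≥ 5; 334, 0.008) = 13.2%.

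At other assumed SPE rates between 0.1% and 3%, with 300 or 334 subjects, the figure at ρ = 1 runs from 3.7% to 12.1%. Discreteness makes the inflation uneven.

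**5. ISO test, subjects over eyes.** Take an assumed SPE rate of 1% and 8 bilaterally affected subjects of 300.
- Subjects over subjects (8/300): p = 0.012.
- Eyes over eyes (16/600): p = 0.0005.
- Subjects over eyes (8/600): p = 0.26.

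The same data give a strong signal or none, depending on which sentence of SAP 15.2 the programmer follows.

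**The case against.** The strongest reply is that nothing formal depends on these tables. H01s, its power and its decision rule are defined on first eyes, and no rule lets an all-eyes result replace a first-eye failure. Study success in SAP 13.1 rests on the two effectiveness endpoints. This stands. A reader might infer that the trial could claim SSI non-inferiority on evidence that fails by first eye; the documents do not allow that.

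Second, eye-level rows for the SSI interval are an inference. The code defines the response per subject. Applied literally to all eyes, it would give 2/334 in both analyses and no contradiction. This also stands: for SAP 15.1 the defect is an unstated unit, and the narrow interval follows only on the eye-level reading.

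Third, a reader might infer that the ISO p-values also err in the lens's favour. As coded they do not: the test is upper-tail, and treating eyes as independent counts against the lens. Only subject counts over an eye denominator would favour it. SAP 15.2 attaches no decision to these p-values; the 5% cut is illustrative, although it is also the default one-sided level in SAP 8.4.

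Fourth, the SSI example is selective. At 334/167, with bilateral test cases only and no control case, one such subject passes both ways and three or more fail both ways. The figures at ρ = 1 are the extreme.

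Last, the redacted text in SAP 8.1 may bear on the matter, so the claim covers visible text only. What survives is that SAP 15.2 writes out an independent-eye test and a counting rule that contradicts it, which is more than missing detail.

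**Conclusion.** The point holds for the supportive all-operative-eyes analyses and goes no further. It should be corrected, but it does not threaten the trial's formal conclusions.

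In SAP 15.2 the code as written gives wrong p-values for all eyes whenever events correlate within subjects: about 4.5%, 8% and 13% false signals at ρ = 0, 0.5 and 1, on the assumed 0.8% SPE rate. The counting rule in the text contradicts the code, and combining the two reverses the bias.

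In SAP 15.1 the interval is too narrow if rows are eyes: size 4.2%, 8.3% and 14.6% at the same correlations with 334/167 subjects, and a possible supportive pass where the first-eye analysis fails. The practical harm is a reported upper limit below 1.4% that seems to corroborate, or to soften, a co-primary safety result while counting the same people twice.

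The sizes rest on assumed values of ρ and of the SPE rate, and on both eyes being implanted in every subject. First-eye and second-eye analyses use one eye per subject and are not affected.

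**What to change.** State the unit for every all-operative-eyes analysis, and choose one of three routes:

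- define the SSI and ISO outcomes at subject level (any eye with the event, N = subjects);
- use a subject-clustered interval that copes with very few events and a likely empty control cell, for which an ordinary GEE is poorly suited;
- report all-eyes results descriptively, with no 0.014 rule and no binomial p-values.

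In SAP 15.2, make the counting rule, the numerator and the denominator use the same unit. In SAP 15.1, say whether the response variable is per eye or per subject in each repeat. Keep the first-eye and second-eye analyses as planned.

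The cost is SAP wording and minor reprogramming, best done before unmasking. Supportive intervals become somewhat wider. Sample size, conduct and the formal tests do not change.

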##### **Co-primary Safety Analyses**

The co-primary safety endpoints are:

- Cumulative rate of SSIs related to the optical properties of the IOL in first operative eyes through Month 12 (Visit 5)
- Mean monocular distance contrast sensitivity (mesopic with and without glare at 1.5, 3, 6, and 12 cpd measured at 2.5m, and photopic with and without glare at 3, 6, 12, and 18 cpd, measured at 2.5m) in first operative eyes at Month 12 (Visit 5)

Descriptive statistics and analyses of co-primary safety variables will be based on first operative eyes and repeated as supportive analyses using second operative eyes as well as all operative eyes.

Secondary surgical interventions related to the optical properties of the IOL will be summarized by descriptive statistics for each IOL group. Noninferiority of FINEVISION HP IOL compared to AcrySof SN60AT [REDACTED] IOL in the proportions of first operative eyes with secondary surgical interventions related to the optical properties of the IOL will be evaluated using two-sided 90% Farrington method confidence intervals around the difference in proportions between the FINEVISION HP IOL and AcrySof SN60AT [REDACTED] IOL. If the upper limit of the confidence interval is less than 0.014, then  $H_{01s}$  will be rejected in favor of  $H_{11s}$  and the FINEVISION HP IOL will be considered statistically non-inferior to the

AcrySof SN60AT [REDACTED] IOL in rate of secondary surgical interventions related to optical properties of the IOL.

Monocular best-corrected distance contrast sensitivity (mesopic with and without glare at 1.5, 3, 6, and 12 cpd measured at 2.5m, and photopic with and without glare at 3, 6, 12, and 18 cpd, measured at 2.5m) in first operative eyes based on the Best Case Set will be summarized by descriptive statistics for each IOL group. The treatment group difference (mean Test group contrast sensitivity minus mean Control group contrast sensitivity) in log units will be presented by testing condition and frequency. Additionally, for each testing condition and frequency, the 5th percentile for the control group log contrast sensitivity will be determined and the percentage of subjects in the investigational arm who have achieved a log contrast sensitivity lower than this value will be reported.

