##### **3.1.2 PRIMARY SAFETY VARIABLES**

The co-primary safety variables are the following:

- Cumulative rate of SSIs related to the optical properties of the IOL in first operative eyes through Month 12 (Visit 5)
- Mean monocular distance contrast sensitivity (mesopic with and without glare at 1.5, 3, 6, and 12 cycles per degree (cpd) measured at 2.5 m, and photopic with and without glare at 3, 6, 12, and 18 cpd, measured at 2.5 m) in first operative eyes at Month 12 (Visit 5)

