## 5. Sample Size and Power Considerations

As specified in ANSI Z80.12:2007 (R2017) –C.4, a minimum of 300 subjects implanted with the investigational IOL and 150 subjects implanted with the comparator IOL must be available for analysis at Visit 5 (postoperative days 330-420).

To consider the potential loss of subjects between the time of enrollment and study completion, a total of approximately 501 subjects will be randomized and undergo surgery in this study. It is assumed that of approximately 501 subjects who undergo surgery, 51 subjects (10%) will be discontinued prematurely or lost to follow-up. Subjects will be randomized to receive either the investigational or comparator IOL in a 2:1 ratio. Of 501 subjects who undergo surgery, approximately 334 subjects will receive the investigational IOL, and 167 subjects will receive the comparator IOL. Expecting a screen failure rate of 7%, up to 539 subjects will be enrolled in the study to have 501 subjects randomized and scheduled for surgery.

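### The planned count of test eyes below the control 5th percentile of contrast sensitivity is 0% by construction wherever more than 5% of controls share the lowest score, and it has no control-arm counterpart.

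*SAP*

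**What the plan says.** Mean monocular contrast sensitivity in first operative eyes at Month 12 is a co-primary safety variable (SAP 3.1.2). It covers mesopic and photopic testing, each with and without glare, at four frequencies per condition: 4 x 4 = 16 cells.

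SAP 15.1 plans three outputs per cell:
- The results "in first operative eyes based on the Best Case Set will be summarized by treatment group using continuous summary statistics".
- The test-minus-control mean difference "in log units will be presented by testing condition and frequency".
- A percentile count: "the 5th percentile for the control group log contrast sensitivity will be determined", and then the "percentage of subjects in the investigational arm who have achieved a log contrast sensitivity lower than this value will be reported".

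Protocol 9.4.6, under the co-primary safety analyses, words the count the same way: "the percentage of subjects in the investigational arm who have achieved a log contrast sensitivity lower than this value will be reported".

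The comparison is strict (lower than), and only the investigational arm is counted. Neither document gives the lowest scorable level, the handling of ties, the percentile definition, or a count of eyes at the lowest score. No hypothesis or limit is attached to contrast sensitivity; the primary safety hypothesis in SAP 3.5.2 concerns secondary surgical interventions only.

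**The concern.** A contrast test has an easiest target. If eyes that cannot see it all receive the same lowest score, the scale has a floor. Once enough controls are there, the control 5th percentile is the floor itself. No test eye can then be counted, and the table prints 0% whether few or most test eyes failed the target.

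The count is the only planned output for this endpoint that looks at individual loss rather than arm-level location and spread. Protocol 2.3.1 lists reduced contrast sensitivity as a known risk of multifocal lenses, and Protocol 2.3.3 weighs it against the benefit. A 0% in that column invites the reading that no excess of test eyes lost contrast, when the cell may simply be unable to show one.

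A lesser problem arises away from the floor. With stepped scores, ties at the cut leave fewer than 5% of controls strictly below it. With no control column, the reader will set the test percentage against a nominal 5% that the control arm does not have.

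**Working it through.** The documents state no expected percentage or power for this count, so there is no figure to reproduce.

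**Inputs from the documents.** The strict rule (SAP 15.1, Protocol 9.4.6). 300 test and 150 control eyes, from the Visit 5 requirement in SAP 5: "a minimum of 300 subjects implanted with the investigational IOL and 150 subjects implanted with the comparator IOL must be available for analysis"; the Best Case Set may be smaller. SAS software (SAP 8.4); no percentile definition is named, so its default is assumed (empirical distribution with averaging).

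**Step 1: the boundary, which needs no assumption about the scale.** With n = 150, 0.05 x 150 = 7.5, so the SAS default takes the 8th lowest control value.
- 8 or more controls at the lowest score (8/150 = 5.33%): the cut equals that score and the strict count is exactly 0%.
- 7 or fewer (7/150 = 4.67%): the cut lies above it.
- If 0.05 x n is whole and exactly 5% are at the floor (7 of 140, 8 of 160), SAS averages two order statistics, the cut lies above the floor, and floor eyes are counted. The condition is therefore more than 5%, not 5% or more.
- Under linear interpolation, 8 of 150 still puts the cut above the floor, but 9 of 150 (6.0%) does not.

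**Step 2: size under assumed values.** Assumed, because the documents give none of them: latent normal scores, SD 0.30 log, rounded down to 0.15-log steps, floor at 0, true test deficit 0.30 log. Any latent value under 0.15 scores 0, so with control mean m:
- share of controls at floor = Φ((0.15 − m)/0.30)
- share of test eyes at floor = Φ((0.15 − (m − 0.30))/0.30)

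For m = 0.45 these are Φ(−1.00) = 15.9% and Φ(0) = 50.0%. For m = 0.55, Φ(−1.33) = 9.1% and Φ(−0.33) = 36.9%. For m = 0.65, Φ(−1.67) = 4.8% and Φ(−0.67) = 25.2%.

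The chance that the cut falls on the floor is the binomial probability of at least 8 of 150 controls there: 96.9% at a rate of 0.0912 and 42.7% at 0.0478. Simulated averages of the planned count (2,000 trials per setting) are:

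| Control mean (log) | Controls at floor | Test eyes at floor | Planned count | Trials giving exactly 0% |
|---|---|---|---|---|
| 0.45 | 15.9% | 50.0% | 0.0% | all |
| 0.55 | 9.1% | 36.9% | 1.2% | about 97% |
| 0.65 | 4.8% | 25.2% | about 14.5% | about 43% |
| 0.80-1.00 | little floor | little floor | about 19-20% | almost none |

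Counting at or below the cut in both arms, the first three rows become 50.0% v 15.9%, 37.5% v 9.4% and 35.6% v 9.0% (test v control). In the last row only about 2.9% of controls are strictly below the cut.

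**Step 3: does the result depend on stepped scores?** A simulation with continuous scores and 10% of controls at the floor gives a strict count of 0.2%, 0.4% and 0.5% for true deficits of 0, 0.15 and 0.30 log. The at-or-below count is 10.0%, 21.8% and 38.9%. The strict count hardly responds to the deficit.

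**Step 4: what the other outputs show.** At control mean 0.45 the mean difference averages −0.23 log against a true −0.30, a compression of (0.30 − 0.23)/0.30 = 23%. Average medians are about 0.38 (control) and 0.07 (test). At control mean 0.55 the difference averages −0.26 log.

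**The case against.** The strongest reply is that nothing is decided by this count. It is an added summary to an endpoint defined as a mean, with no hypothesis and no limit. That stands. A reader might infer that the lens could pass a safety criterion falsely; the documents contain no such criterion for contrast sensitivity.

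A reader might also infer that the loss would be hidden. It would not be. SAP 8.4 requires mean, SD, median, minimum and maximum, and SAP 15.1 gives these by arm with the mean difference. Step 4 shows a clear deficit even where the count is 0%. What remains is that these outputs are themselves compressed and do not say how many eyes are affected.

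Third, it is tempting to name mesopic 12 cpd and photopic 18 cpd with glare as the affected cells. They are plausible, but the documents contain nothing on control score distributions. The Best Case Set also excludes clinically significant preoperative ocular pathology in the first operative eye, which makes substantial control floor rates less certain. The control means of 0.45 and 0.55 were chosen to lie near an assumed floor.

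Finally, scoring of an unseen target may be set in the Manual of Procedures, and further analysis detail in the ISO and ANSI standards that Protocol 9.4.3 cites. None of these is available here, so the absence of a floor score is not counted as a fault. A floor score alone would not cure the strict inequality or supply the control percentage.

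**Conclusion.** The point holds as a conditional statement about a descriptive table. Where more than 5% of controls share the lowest score (8 or more of 150 under the SAS default), the planned count is 0% whatever happens in the test arm. That part is arithmetic and needs only the strict wording and the percentile definition.

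The size rests on the assumed SD, step, floor and deficit: from about 19-20% with little floor to 0% with about 16% of controls at the floor. Near the boundary the answer turns on one or two control eyes. Away from the floor the effect is small: with these steps the true control reference is about 2.9% rather than 5%, so the excess is understated by about 2 points. How many of the 16 cells are affected, if any, cannot be told from the documents. The change is worth making because it is cheap and because a 0% forced by the rule is easily misread in a co-primary safety table; the trial's conclusions do not depend on it.

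**What to change.** In SAP 15.1, for each condition and frequency:
1. Report in both arms the percentage of eyes strictly below the control 5th percentile, at or below it, and at the lowest score, each with the test-minus-control difference.
2. Where the control 5th percentile equals the lowest score, present the at-floor difference as the individual-level loss summary for that cell.
3. Name the percentile definition, and cite the place where the lowest score is defined (the Manual of Procedures, if it is already there).

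This should be written before unmasking, so that the choice of count is not made with the results in view. It uses data already collected. The cost is SAP wording and additional table columns, and some cells may look less favourable to the test lens than under the present rule.
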